## STATISTICAL CONSIDERATIONS

This study will enroll patients with PCR confirmed COVID according inclusion criteria.

The trial has three groups, each with 10 subjects (n=30). All eligible study subjects will be randomized, double-blinded, to either the two treatment groups or placebo group. Two main groups will be provided with exosomes in a specially provided solution, the third group (control) will receive the same solution without exosomes. Due to exosomes are nanoparticles and requires special methods and devices to be detected the hospital staff and patients have no way to check which group receives exosomes.

This is interventional, prospective, randomized double-blinded with a control group study.

The primary outcomes will be assessed at discharge of the clinic and 1 month after. Duration of study participation will be 1 months from the time of discharge from the clinic.

It is estimated that up to 2-3 research participants will be enrolled each week and that approximately 4 weeks of accrual will be necessary to enroll 10 participants.

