## Study Design

Study Type: Interventional

Primary Other

Purpose:

Study Phase: Phase 1/Phase 2 Interventional Parallel Assignment

Study Model: The trial has three groups, each with 10 subjects (n=30). All eligible study subjects

will be randomized, double-blinded, to either the two treatment groups or placebo

group.

Number of 3 Arms:

Masking: Double (Participant, Care Provider)

Two main groups will be provided with exosomes in a specially provided solution, the third group (control) will receive the same solution without exosomes. Due to exosomes are nanoparticles and requires special methods and devices to be detected the hospital staff and patients have no way to check which group receives

exosomes.

Allocation: Randomized Enrollment: 30 [Actual]

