## **Eligibility**

Minimum Age: 18 Years

Maximum 65 Years

Age:

Sex: All

Gender No

Based:

Accepts No Healthy

Volunteers:

Criteria: Inclusion Criteria:

- Ability to understand the study objectives and risks and provide signed and dated informed consent;
- Confirmed COVID-19 infection (by PCR or antibody test);
- Pneumonia requiring hospitalization, and oxygen saturation of <94% indoors or a need for auxiliary oxygen. The confirmed volume of lung damage by CT: not less than 30% and not more than 80%;
- · ability to proceed with inhalation by self;

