#### **Exclusion Criteria:**

• Severe respiratory failure at the time of screening due to COVID-19 pneumonia;

- Known to undergo medical resuscitation for 14 days before randomization;
- Any serious medical condition or deviation of the clinical laboratory parameter that, in the opinion of the researcher, prevents safe participation and completion of the study by the participant Confirmed uncontrolled active bacterial, fungal, viral or other infection (other than SARS-CoV-2).
- According to the researcher, the progression to death is inevitable and will occur within the next 24 hours, regardless of the therapy.
- The life expectancy of fewer than 28 days, taking into account a medical condition already existing that cannot be corrected, e.g. participants with the following conditions or suspicions: polyorganic insufficiency, poorly controlled neoplasms, terminal stage heart disease, cardiopulmonary cardiac arrest that required cardiopulmonary resuscitation, or electrical activity not accompanied by a pulse, or asystole within the last 30 days, terminal stage liver disease, terminal stage liver disease, or liver disease;
- · Pregnancy or breastfeeding;
- Liver function failure (Class C for Child-Pugh), detected within 24 hours at screening (local laboratory);
- Absolute neutrophil count (ANC) <500 cells/µL at screening (local laboratory);

- Platelet count <50000 cells/µL at screening (based on laboratory data);

- Creatinine level ≥ 1.5 from the upper limit;
- Uncontrolled or untreated arrhythmia with clinical manifestations, myocardial infarction within the last 6 weeks or congestive heart failure (NYHA Degrees 3 or 4);
- Respiratory failure in the last 6 months or home use of oxygen in severe chronic respiratory disease (COPD);
- Quadriplegia;
- Primary immunodeficiency, tuberculosis, progressive multifocal leukoencephalopathy, aspergillosis or other invasive mold/fungal infection in anamnesis, or internal or bone marrow transplantation for 6 months before randomization;
- Known infection with hepatitis B or C viruses requiring therapy;

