#### **Demographics and Baseline Characteristics**

Demographics and baseline characteristics will be summarized for all research participants. Characteristics to be examined include age, sex. The results will be statistically processed using parametric and non-parametric statistics methods using STATA version 9.0, Statistica for Windows version 6.0 and MS Office Excel 2007. Changes from the start of therapy and after will be compared using the T-test, comparing data between the main group and the control group using non-parametric method, box-plot.

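### Does describing the patients as PCR-confirmed, when eligibility also accepts an antibody test, leave the analysis population undefined?

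*Combined protocol and SAP*

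**What the plan says.** All references are to the combined protocol and SAP.

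- **STATISTICAL CONSIDERATIONS**, on who is enrolled: "This study will enroll patients with PCR confirmed COVID according inclusion criteria". The same section gives the size as "The trial has three groups, each with 10 subjects (n=30" and sends all eligible subjects to randomisation.
- **Eligibility**, inclusion criteria: "Confirmed COVID-19 infection (by PCR or antibody test"; either test is enough. Every patient must also have pneumonia needing hospital care, with low oxygen saturation or a need for oxygen, and CT lung involvement between 30% and 80%.
- **Exclusion Criteria**: the infection exclusion is "Confirmed uncontrolled active bacterial, fungal, viral or other infection (other than SARS-CoV-2". It says nothing about patients who are positive by antibody only.
- **Demographics and Baseline Characteristics**: "Characteristics to be examined include age, sex".
- **Study Design**: "Enrollment: 30 [Actual".
- **STATISTICAL CONSIDERATIONS**, on accrual: at two to three patients a week, "approximately 4 weeks of accrual will be necessary to enroll 10 participants".

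**The concern.** The statistical section points to the inclusion criteria and then states them more narrowly than they stand. A patient with a positive antibody test and no positive PCR is eligible under one section and outside the population described in the other. No other section reconciles the two, and the history of changes lists a single revision, so this is not leftover text from an amendment.

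Two things would be at stake. First, a report that followed the statistical section could call the whole sample PCR-confirmed when some patients were not. Second, in arms of 10, antibody-only patients could fall unevenly by chance, and a baseline table limited to age and sex would not show it. The accrual sentence adds to the impression of loose drafting, since it gives a time for 10 participants in a trial of 30.

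**Working it through.** **1. Which text governs enrolment.** Eligibility is the only place that lists entry criteria. The statistical sentence cites those criteria and does not replace them, and randomisation is of all eligible subjects. Read together, the set randomised is the set that met the Eligibility list, and the statistical sentence is an incomplete paraphrase of it.

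**2. Whether any analysis depends on PCR status.** The table in Research methods and STATISTICAL CONSIDERATIONS plans:

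| Outcome | Planned treatment of the data | Uses PCR status? |
|---|---|---|
| Side effects | Percentage of all patients in the group | No |
| CRP, LDH | Within-group t-test, baseline to day 11 | No |
| Time to clinical recovery (days in hospital) | Mean and SD | No |
| SpO2 | Daily medians; t-test within and between groups | No |

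There is no viral endpoint, no PCR-positive subset and no stratification by route of confirmation.

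**3. Size of a possible chance imbalance.** The number of antibody-only patients, k, is not in the documents, so k = 2, 3 and 6 are assumptions. With k of 30 patients allocated at random to arms of 10, 10 and 10,

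P(a, b, c) = C(10,a)·C(10,b)·C(10,c) / C(30,k), with a + b + c = k,

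where a is the count in a given exosome arm, b in placebo and c in the third arm. Summing over |a − b| ≥ 2:

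- k = 2: 2·45 / 435 = 0.207
- k = 3: 2·(45·10 + 120) / 4060 = 1140 / 4060 = 0.281
- k = 6: 246000 / 593775 = 0.414

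The formula contains only k and the arm size. It would give the same values for any yes/no trait carried by k of the 30, so it describes arms of 10 and not this wording. It counts patients; it does not measure bias in an outcome.

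**4. What a PCR-positive sensitivity analysis could show.** Assume 80% power and two-sided 5%, neither of which is in the documents. The detectable standardised difference d makes the power of a two-sample t-test (2n − 2 degrees of freedom, noncentrality d·√(n/2)) equal to 0.80. It is 1.32 SD at 10 v 10, 1.51 SD at 8 v 8 and 1.80 SD at 6 v 6. The smaller sizes assume equal losses from the two arms. The full comparison is already coarse, and the restricted one is coarser.

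**5. Accrual.** Ten participants at two to three a week take 10/3 = 3.3 to 10/2 = 5 weeks, which agrees with about four weeks for one group of 10. Thirty would take 30/3 = 10 to 30/2 = 15 weeks. The sentence is consistent if it refers to one group. It is a forecast with no bearing on the analysis, and enrolment is recorded as complete.

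**The case for a change.** The best case for a change is that a statistical plan should say correctly whom it studies, and this one says two things. Since enrolment is finished, each patient's route of confirmation is already a fact in the screening records. Aligning the wording and adding one baseline row by arm would cost almost nothing. The imbalance figures are also mild as stated: the chance that at least one of the two exosome arms differs from placebo by two or more antibody-only patients is 31%, 53% and 66% at k = 2, 3 and 6, and two patients are a fifth of an arm.

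Part of this stands. The texts do disagree, and a report should not call the whole sample PCR-confirmed if it was not. The rest does not lead to a change:

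- The baseline list is introduced as what is included, so it does not bar a row on confirmation route. If it were exhaustive, it would also omit CT extent and oxygen status, which the entry criteria use to define severity. A short baseline table is a separate and more general matter.
- Nothing in the documents links route of confirmation to prognosis or to response. The stated rationale is anti-inflammatory and regenerative, and the severity requirements apply to everyone. Randomisation rules out systematic placement of antibody-only patients in one arm.
- Amending the eligibility text after the patients are in would rewrite a criterion retrospectively, for no analytical gain.

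**Conclusion.** This is a clerical inconsistency that needs no change to the plan. The population analysed is the randomised patients who met the Eligibility list, and neither reading of the confirmation wording alters a planned estimate, test or sample size. Any effect on outcomes is unknown and may be nil, since the documents do not show that any antibody-only patient was enrolled; the 21% to 41% imbalance probabilities rest on assumed values of k and apply to any trait of that frequency. An analyst would handle the point in ordinary reporting: describe patients by the criterion that was applied and, if any qualified by antibody alone, give their number by arm. This conclusion assumes that enrolment followed the Eligibility section and that no unstated analysis restricts to PCR-positive patients. If such a restriction were introduced, the wording would matter.

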## **Arms and Interventions**

Arms	Assigned Interventions	
Experimental: EXO-1 Participants (n=10) in this group will receive standard therapy and exosomes of the first type.	Procedure/Surgery: EXO 1 inhalation Twice a day during 10 days inhalation of 3 ml special solution contained 0.5-2x10^10 of nanoparticles (exosomes) of the first type.	
Experimental: EXO-2 Participants (n=10) in this group will receive standard therapy and exosomes of the second type.	Procedure/Surgery: EXO 2 inhalation Twice a day during 10 days inhalation of 3 ml special solution contained 0.5-2x10^10 of nanoparticles (exosomes) of the second type.	
Placebo Comparator: Placebo Participants (n=10) in this group will receive standard therapy and inhalation placebo solution.	Procedure/Surgery: Placebo inhalation Twice a day during 10 days inhalation of 3 ml special solution free of nanoparticles (exosomes).	

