#### Research methods and STATISTICAL CONSIDERATIONS

Title	Purpose	Method	Frequency	Statistics
Number of	Safety	Collection of	After each	Numeric data, calculated
participants with minor and serious side effects	assessment of the procedure.	information about unwanted reactions to inhalation, for example, 1) temperature increase, 2) allergic reaction in the form of swelling Quincke, rash, seizures, etc.; 3) bronchospasm for inhalation	procedure	as a percent from whole patients in the group.
Biochemistry of blood	Evaluation of procedure efficiency	C-reactive protein, LDH	At the beginning of inhalation (day 1) and on next day of last inhalation (day 11)	The difference in each group between baseline and day 11 will be measured by T-test. The data will be presented as a Mean with full range (minmax). The difference will be calculated as Mean

				difference with Standard Deviation (SD)
Time to Clinical Recovery (TTCR)	Evaluation of procedure efficiency	Calculation of days in hospital	Once at the end of trial	The data will be presented as a Mean with Standard Deviation (SD)
SpO2 Concentration Changes	Evaluation of procedure efficiency	The concentration of SpO2 by Pulse oximetry device during procedures and compared to placebo.	Before and after each inhalation (total 4 measures per day). 10 days.	The intraday data (4 measures per day) will be calculated as a Median by day. The Median by day data (10 measures) will be processed by T-test intragroup and between groups. The data in tables will be presented as a Median (Me) with 25-75 quartile range.

The results will be statistically processed using parametric and non-parametric statistics methods using STATA version 9.0, Statistica for Windows version 6.0 and MS Office Excel 2007. Changes from the start of therapy and after will be compared using the T-test, comparing data between the main group and the control group using non-parametric method box-plot (data are presented in Me - median format with an indication of 25% (q1) and 75% (q3) quartile.

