#### **Study Duration**

Research participants will be followed for safety for 1 months after the discharge from the clinic.

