## **EXPECTED RESULTS**

It is assumed that the inhalation method of injection of exosomes will speed up the rehabilitation of patients, reduce the volume of pulmonary tissue lesions and reduce the time of stay of patients in hospital conditions.

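### Primary assessments and the end of safety follow-up hang on discharge, which treatment is expected to shift and which in-hospital deaths never reach; TTCR has no rule for those deaths

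*Combined protocol and SAP*

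**What the plan says.** The section STATISTICAL CONSIDERATIONS sets the timing: "The primary outcomes will be assessed at discharge of the clinic and 1 month after". It closes participation on the same clock: "Duration of study participation will be 1 months from the time of discharge from the clinic". The section Study Duration repeats this for safety: "Research participants will be followed for safety for 1 months after the discharge from the clinic". Neither section gives an assessment day or a follow-up end counted from randomisation or first inhalation.

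Two other places make discharge an outcome. EXPECTED RESULTS anticipates that exosomes will "reduce the time of stay of patients in hospital conditions". The table in Research methods and STATISTICAL CONSIDERATIONS defines TTCR by "Calculation of days in hospital", summarised as a mean with SD.

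The other three rows of that table run on the dosing clock. Inhalation reactions are collected after each procedure, CRP and LDH are measured on days 1 and 11, and SpO2 is taken "Before and after each inhalation (total 4 measures per day). 10 days". No row is scheduled at discharge or 1 month later, and no row is labelled primary. No rule covers a patient who dies in hospital or is not discharged.

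**The concern.** An assessment time should not depend on what happens to the patient after randomisation. Here it does, and the event in question is one that treatment is meant to change. Two consequences follow.

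- **Safety window.** Its start is common to all patients, but its end is stay plus 1 month. An arm that goes home sooner is watched for less time after first dosing and can show fewer late events for that reason alone. Safety is reported as a crude percentage of patients, with no allowance for time observed.
- **Deaths.** A patient who dies in hospital has no discharge, so neither primary time point exists for that patient. TTCR has no defined value either. If the analyst simply counts days in hospital, a death on day 10 enters as a 10-day stay, which looks like fast recovery. If the patient is dropped, the death disappears from the efficacy result. In a trial of hospitalised pneumonia, either choice could favour the arm with more deaths.

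**Working it through.** The documents derive no figure on this point (no effect size, event rate, mortality or expected stay), so there is nothing to reproduce. The sizes below rest on assumptions, labelled as such.

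**Inputs from the documents:** three arms of 10, N = 30; 10 days of inhalation in every arm; follow-up to 1 month after discharge; TTCR as a mean.

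**Assumptions:** 1 month = 30 days; stay counted from first inhalation; placebo stay 20 days; exosome stay shorter by 2, 5 or 8 days; constant event hazard, the same in both arms; 30% event risk on placebo over its full window; in-hospital mortality 2% to 20%.

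**1. Unequal windows.** Window = stay + 30 days. Placebo: 20 + 30 = 50 days. The hazard giving 30% over 50 days is h = −ln(0.70)/50 = 0.00713 per day. Apparent risk over w days is 1 − exp(−h·w).

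| Stay shorter by | Window | Reduction | Apparent risk | Spurious gain |
|---|---|---|---|---|
| 2 days | 48 days | 4% | 29.0% | 1.0 point |
| 5 days | 45 days | 10% | 27.5% | 2.5 points |
| 8 days | 42 days | 16% | 25.9% | 4.1 points |

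In an arm of 10, 4.1 points is 0.41 of a patient. With placebo stays from 14 to 25 days, the reduction in window runs from 3.6% (2/55) to 18.2% (8/44).

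**2. Chance that a death occurs.** P(at least one) = 1 − (1 − p)^n.

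| Assumed mortality p | One arm, n = 10 | All, n = 30 | Expected deaths in 30 |
|---|---|---|---|
| 2% | 18.3% | 45.5% | 0.6 |
| 5% | 40.1% | 78.5% | 1.5 |
| 10% | 65.1% | 95.8% | 3 |
| 20% | 89.3% | 99.9% | 6 |

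**3. What one death does.** It removes 1/10 = 10% of an arm from both discharge-based time points. If the death is counted as a stay, a death on day d in an arm whose other nine patients average m days moves the mean by (d − m)/10. With d = 10 (last dosing day) and m = 20, that is (10 − 20)/10 = −1.0 day, an apparent benefit of a full day from one death.

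**4. The two schedules side by side.** The methods table has three rows on dosing days or procedures and one duration (TTCR). The later section has unnamed primary outcomes at discharge and 1 month after. No tabulated variable matches either of those two time points, so the two sections cannot both be the outcome schedule.

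**The case against.** The strongest reply is that the table, the only place where outcomes are defined, already puts most of them on a common clock. That is correct, and it rules out several broader conclusions.

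- A reader might infer that the arms are compared throughout at different times since dosing. They are not: CRP/LDH, SpO2 and inhalation reactions have fixed days or procedures, and a patient who later dies still contributes data up to death.
- A reader might infer that assessing at discharge makes the arms alike and hides the speed of recovery. The documents give no discharge criteria to support the first part, and TTCR measures speed directly.
- A reader might infer that only discharged survivors are analysed. The safety percentage is taken over all patients in the group, so a patient who dies stays in that denominator.
- The window effect is small and rests on assumed stays. The one tabulated safety variable, reactions to inhalation, is collected around procedures and is not exposed to it.
- Eligibility lowers the risk of death: severe respiratory failure, inevitable death within 24 hours, and life expectancy under 28 days from existing conditions are excluded.

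All of this narrows the point without removing it. The later sections still state a discharge-based rule for the primary outcomes and for the end of safety follow-up. The exclusions do not rule out death from COVID-19 after randomisation in patients who need hospital care and have 30% to 80% lung damage on CT. TTCR still has no rule for such a death.

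**Conclusion.** The point holds for three things: the discharge-based primary assessments, the end of the safety window, and TTCR. It does not extend to the outcomes tied to dosing.

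The unequal window by itself is minor, under half a patient per arm of 10 under the assumptions above. The missing rule for in-hospital death is the larger matter. Even at 2% assumed mortality, a death somewhere in the trial is nearly an even chance, and at 5% to 10% it is likely. With 10 patients per arm, one such patient can visibly move a mean stay. The documents give neither mortality nor stays, so these figures show scale and are not predictions.

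Separately, and without any assumption, the methods table and STATISTICAL CONSIDERATIONS disagree on when outcomes are assessed and must be reconciled. This should be changed.

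**What to change.** 1. In STATISTICAL CONSIDERATIONS and Study Duration, set the between-arm assessment and the safety comparison at the same fixed days from randomisation for all 30 patients. Day 11 is already a measurement day; about day 40 (10 days of inhalation + 30) would serve as the later one.
2. On each of those days record every patient's status, including dead and still in hospital.
3. Count TTCR from randomisation, and treat in-hospital death as the worst rank or as a competing event, never as a short stay. State the rule for patients not yet discharged.
4. Align the methods table with these days and say which outcomes are primary.
5. Keep the contact 1 month after discharge, and list safety events after the common day separately.

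**Cost.** Protocol wording and at most one extra telephone contact per patient. Events after the common day leave the between-arm comparison: with assumed stays of 11 to 30 days, follow-up now ends on day 41 (11 + 30) to day 60 (30 + 30), so a day-40 cut moves 1 to 20 days of it to the listing. The Study Design section gives enrolment of 30 as actual, which suggests recruitment is finished. If follow-up is also complete, apply the common day in the analysis to the data already collected, and fix that day before allocation is revealed.
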